8.2.3.2. Specimen Shipment

Specimen shipment will occur at intervals during the course of this study following all applicable International Air Transport Association (IATA) requirements and according to the specifics for storage temperature and documentation as detailed in the central (clinical) laboratory manual and protocol-specific MOP as appropriate.

Specimens for safety laboratory evaluations will be transported from the participating site to the local site laboratory.

Specimens for *Coccidioides* antibodies and fluconazole serum levels will be shipped from the participating sites to the DMID Clinical Repository and provided to ARUP laboratories and UC Davis in a blinded manner.

The frequency and conditions of specimen shipment will be described in the appropriate section of the MOP.

9. ASSESSMENT OF SAFETY

9.1. Specification of Safety Parameters

Fluconazole is an approved drug with an established and well-described safety profile. The most prevalent of the drug side effects include headache (13%), nausea (7%), and abdominal pain (6%). In less than 1% of individuals taking this medication there is a perversion of taste. There are rare reports of exfoliative dermatitis, some of which were fatal. There are reports of liver toxicity (in particular with patients with co-morbidities and previous liver injury), which are not dose dependent.

As fluconazole is an approved drug with a long prescribing history, NIAID does not expect that any new drug related safety signal will be detected in this trial. As such, the safety data collection will be targeted to only collect Suspected Unexpected Serious Adverse Reactions (SUSARs) and congenital anomalies/birth defects.

For individual patients, liver function testing will be performed to monitor for possible liver injury.

9.2. Methods and Timing for Assessing, Recording, and Analyzing Safety Parameters

9.2.1. Adverse Events

Adverse Event (AE): International Conference on Harmonisation (ICH) E6 defines an AE as any untoward medical occurrence in a patient or clinical investigation subject administered a pharmaceutical product regardless of its causal relationship to the study treatment. FDA defines an AE as any untoward medical occurrence associated with the use of a drug in humans, whether or not considered drug related. An AE can therefore be any unfavorable and unintended sign (including an abnormal laboratory finding), symptom, or disease temporally associated with the use of a medicinal (investigational) product.

As the safety profile of fluconazole is well established, and this trial is not powered to detect new, unknown safety signals, **there will be no non-serious AE collection in this trial.**

Relationship to Study Products: The licensed study physician's assessment of a SAE's relationship to study product is part of the documentation process, but it is not a factor in determining what is or is not reported in this trial. If there is any doubt as to whether a clinical observation is an SAE, the event should be reported. The relationship to study product must be assessed for SAEs using the terms: related or not related. In a clinical trial, the study product must always be suspect. To help assess, the following guidelines are used:

-
- **Related** – There is a reasonable possibility that the study product caused the adverse event. Reasonable possibility means that there is evidence to suggest a causal relationship between the study product and the adverse event.
 - **Not Related** – There is not a reasonable possibility that the administration of the study product caused the event.

9.2.2. Serious Adverse Events

Serious Adverse Event (SAE): An adverse event or suspected adverse reaction is considered “serious” if, in the view of either the investigator or sponsor, it results in any of the following outcomes:

- Death
- A life-threatening adverse event*
- Inpatient hospitalization or prolongation of existing hospitalization
- A persistent or significant incapacity or substantial disruption of the ability to conduct normal life functions, or
- A congenital anomaly/birth defect
- Important medical events that may not result in death, be life-threatening, or require hospitalizations may be considered serious when, based upon appropriate medical judgment they may jeopardize the patient or subject and may require medical or surgical intervention to prevent one of the outcomes listed in this definition. Examples of such medical events include allergic bronchospasm requiring intensive treatment in an emergency room or at home, blood dyscrasias or convulsions that do not result in inpatient hospitalization, or the development of drug dependency or drug abuse

*Life-threatening adverse event. An adverse event is considered “life-threatening” if, in the view of either the site principal investigator or sponsor, its occurrence places the patient or subject at immediate risk of death. It does not include an adverse event that, had it occurred in a more severe form, might have caused death.

Death and life-threatening events are part of the efficacy endpoints of this trial and will not be reported or collected as SAEs unless they meet the criteria below.

Only the following events will be considered SAEs:

- Congenital anomalies or birth defect, OR
- Any condition that meets the regulatory definition of a SAE AND is unexpected (per PI) AND is suspected to be directly caused by the study drug (e.g., anaphylaxis, Stevens-Johnson syndrome, exfoliative dermatitis)

Protocol defined SAEs will be:

- Collected from the time of enrollment through visit Day 49
- Assessed for relationship to study product
- Recorded on the appropriate SAE form and eCRF
- Followed through resolution by a licensed study physician listed on the Form FDA 1572 as the site principal investigator or sub-investigator
- Reviewed and evaluated by DMID, the DSMB (periodic review), and the IRB

9.2.3. Procedures to be Followed in the Event of Abnormal Laboratory Test Values or Abnormal Clinical Findings

Study drug will be stopped for the individual subject if:

- If any of the following criteria for liver-related adverse events are met and confirmed:
 - AST elevation of >5X ULN or greater than or equal to 225 IU/L or
 - ALT elevation of >5X ULN or greater than or equal to 250 IU/L or
 - Total bilirubin elevation >1.5X ULN or
 - Aminotransferase elevation of >3X ULN accompanied by total bilirubin elevation >1.5X ULN
- If any subject experiences any of the following:
 - QTc prolongation as defined by a corrected QT of > 500ms OR > 60ms above baseline measurement
 - Torsades de pointes (torsades, TdP)
 - Unexplained Syncope
 - Seizure in non-epileptic patients

The subject will be referred to an appropriate health care provider for treatment, and will be followed-up until stabilization or resolution.

The abnormal hepatic function testing will be documented on an appropriate eCRF.

Aggregate information regarding abnormalities of hepatic function testing will be presented to the DSMB in their regular meetings.

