3.2.2. Secondary

See Section 11.4.4.2 for a discussion of the analysis populations utilized for the secondary outcome measures.

Secondary Outcome 1:

- The proportion of subjects who achieve a clinical response at Day 22 in each treatment group, including in all randomized subjects who took at least one dose of study medication.
 - “Clinical response” is defined as at least a 50% reduction in composite FLEET CAP score from baseline.

Secondary Outcome 2:

- The proportion of subjects who achieve a clinical response at Day 43 in each treatment group, including in all randomized subjects who took at least one dose of study medication.
 - “Clinical response” is defined as at least a 50% reduction in composite FLEET CAP score from baseline. Note that a subject who responds earlier before Day 43 does not need to achieve a clinical response at Day 43, as well.

Secondary Outcome 3:

- The mean, median, and quartiles of the FLEET CAP score at Days 22, 29 and 43 in each treatment group.
- The mean, median, and quartiles for each component of the FLEET CAP score at Days 22, 29 and 43 in each treatment group.
 - Cough
 - Fatigue
 - Chest Pain
 - Dyspnea (Shortness of breath)
 - Sputum production
 - Night Sweats
 - Fever
 - Hypoxia

Secondary Outcome 4:

-
- Number of days of school or work missed due to illness after the start of the treatment through Day 43 in each treatment group.
 - The mean, median, and quartiles for the mental component summary (MCS) and physical component summary (PCS) scores of the SF-12v2 instrument and the responses to the individual items of the PROMIS Item Bank v2.0 - Ability to Participate in Social Roles and Activities - Short Form 4a at Days 22, 29, 43, 90 and 180 in each treatment group.

Secondary Outcome 5:

- Incidence rate of all-cause mortality after the start of treatment and through Day 43 by treatment group.
 - Mortality information will be obtained through medical records or next of kin.

Secondary Outcome 6:

- The proportion of subjects who achieve a clinical response at Day 22 among all randomized subjects, regardless of coccidioidomycosis status or adherence to study drug, in each treatment group.

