7.3. Follow-up (Days 22-180, Visits 02-07)

7.3.1. Follow-up Visit Visit 02 (Day 22):

(Window: Day 20 to Day 23):

- Interview subjects and review the medical record for interim medical history, including an assessment for new medical conditions and symptoms, hospitalizations, diagnosis of disseminated coccidioidomycosis. Note any changes since the previous clinic visit.
- Perform a urine or serum pregnancy test on all women of childbearing potential. The test must be negative to ensure continued eligibility.
- Review any concomitant medications since previous study visit. Record all concomitant medications on the appropriate data collection form.
- Review of inclusion/exclusion criteria by clinician licensed to make medical diagnoses to determine continued eligibility.

-
- Perform a targeted physical examination if indicated based on review of complete medical history and any updates obtained by interview of subjects since the Day 1 visit by a clinician licensed to make medical diagnoses.
 - Record vital sign measurements (sitting blood pressure, sitting heart rate, respiratory rate, oral temperature, oxygen saturation and weight).
 - Query subject regarding whether the subject has taken their dose for today. If the subject has not yet taken their dose for today, subject should be instructed to take the day's dose in the clinic, prior to the pill count.
 - Perform a pill count of study product (fluconazole or placebo) and interview to determine adherence. Review need to bring pill bottles for count to each visit, study product dosing and storage requirements and ability to meet requirements with subject.
 - Following pill count, collect the pill bottle A and retain until study product accountability has been completed by the study monitor.
 - Note any discrepancies between expected and actual pill count remaining in pill bottle B.
 - Review randomization number assigned at Visit 01 and dispense final bottle (bottle C) of study product. Instruct the subject to continue to take daily doses from pill bottle B and to begin taking their daily doses from the newly dispensed bottle (bottle C) once bottle B is empty.
 - If subject did not return the pill bottle A dispensed at Visit 01, instruct them to return this bottle at their next visit.
 - Complete FLEET CAP Score
 - Collect the number of days missed from school and/or work due to illness for subjects who were either enrolled in school or employed at baseline

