11.4.3. Safety Analysis Plan

Safety evaluations will be based on the incidence, severity, and type of clinically significant physical examination findings, clinically significant vital signs, and SAEs as defined in Section 9.2.2. Safety variables will be tabulated and presented for all subjects in the safety population, grouped by treatment group.

SAEs will be coded by the Medical Dictionary for Regulatory Activities (MedDRA) for preferred term and system organ class. The rate and exact 95% confidence intervals of related SAEs in aggregate, and by MedDRA categories, will be computed. The number of SAEs will be reported by a detailed listing showing the type, MedDRA coding, relevant dates (administration and adverse event), severity, relatedness, and outcome for each event.

Laboratory toxicities will be analyzed by taking the most severe response over the follow-up period, dichotomizing into a binary variable (none or mild versus moderate or severe) and using exact confidence intervals to summarize the event and toxicity rates. Tabular and graphical summaries of events will be presented for each solicited symptom, by type, severity (none, mild, moderate, severe), and time point post-administration.

Laboratory and vital sign data will also be presented as change from baseline. Variable transformations will be applied as appropriate. Shift tables may be produced for select laboratory parameters.

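### Section 9.2.2 calls life-threatening events efficacy endpoints, but only death is one, so most hospitalisations and non-fatal life-threatening events have no planned by-arm summary

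*Combined protocol and SAP*

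**What the plan says.** Section 9.1 limits safety collection: "the safety data collection will be targeted to only collect Suspected Unexpected Serious Adverse Reactions (SUSARs) and congenital anomalies/birth defects". Section 9.2.1 drops non-serious adverse events altogether. Section 9.2.2 first gives the usual regulatory definition of an SAE, then says: "Death and life-threatening events are part of the efficacy endpoints of this trial and will not be reported or collected as SAEs". It makes an exception for events that satisfy its own narrower list. One entry on that list is congenital anomalies. The other, which requires study drug to be the suspected cause, reads in part: "Any condition that meets the regulatory definition of a SAE AND is unexpected (per PI) AND is suspected to be directly caused by".

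On efficacy, Secondary Outcome 5 (Section 3.2.2) is: "Incidence rate of all-cause mortality after the start of treatment and through Day 43 by treatment group".

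On analysis, Section 11.4.3 says: "Safety evaluations will be based on the incidence, severity, and type of clinically significant physical examination findings, clinically significant vital signs, and SAEs", and it ties the SAEs to the definition in Section 9.2.2. It also covers laboratory toxicities.

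On data capture, the visits at Days 22, 29 and 43 (Sections 7.3.1 to 7.3.3) require staff to interview the subject and "review the medical record for interim medical history, including an assessment for new medical conditions and symptoms, hospitalizations". Hospitalisation for the pneumonia episode more than 72 hours after randomisation, and need for assisted ventilation, are triggers for stopping treatment and for rescue (Sections 5.3.3.1 and 6.7).

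On relatedness, Section 9.2.1 says of the physician's causality assessment that "it is not a factor in determining what is or is not reported in this trial".

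**The concern.** The reason given for leaving life-threatening events out of SAE collection is that the efficacy analysis will count them. If it does not, they drop out of both analyses unless the investigator judges them unexpected and suspects the drug.

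This matters in this design. Section 11.2.1 assumes that 20% of enrolled subjects are cocci-positive, so about 0.80 × 500 = 400 of the planned 500 fluconazole recipients would take an antifungal without the target infection. Section 2.3.1 itself describes a QT interaction risk with antibacterials commonly used for pneumonia. Comparing serious events by randomised arm, whatever their attribution, does not depend on the investigator's opinion of cause. Filtering on expectedness and suspected causation gives up that advantage for events that sites are already told to ask about.

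**Working it through.** **1. Do the endpoints contain what Section 9.2.2 says they contain?**

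| Source | What is measured | Death | Non-fatal life-threatening event | Hospitalisation |
|---|---|---|---|---|
| 3.2.1, primary | FLEET CAP response, Day 22 | no | no | no |
| 3.2.2, Secondary 1, 2, 3, 6 | FLEET CAP response or scores | no | no | no |
| 3.2.2, Secondary 4 | Days missed, SF-12v2, PROMIS | no | no | no |
| 3.2.2, Secondary 5 | All-cause mortality to Day 43 | yes | no | no |
| 3.2.3, Exploratory 1 to 9 | Antibody timing, extra-pulmonary score, dissemination, FLEET CAP summaries, alternative case definition, liver tests, adherence, drug level | only where Exploratory 5 repeats Secondary 5 | no | no |

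Table 11 adds nothing to this list. The rationale in Section 9.2.2 is true for death and untrue for non-fatal life-threatening events.

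**2. Does the safety analysis pick up the remainder?** Take a hospitalisation that the investigator judges unrelated to study drug. It meets the regulatory definition of serious but fails the causation condition in Section 9.2.2, so it is not a protocol SAE. It has no route as a non-serious event, because none are collected. Section 11.4.3 tabulates only SAEs under the Section 9.2.2 definition. The event is in the interim history but in no planned by-arm summary of such events. A non-fatal life-threatening event judged expected follows the same path.

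**3. What partial cover is there?**
- Liver-test elevations are Exploratory Outcome 7 and also fall under the laboratory toxicity analysis in Section 11.4.3.
- QT prolongation, torsades, sudden cardiac death, unexplained syncope and seizure count toward halting rule B in Section 9.5. The count runs over all randomised subjects, not by arm.
- Sections 9.6.2 and 11.3.1 allow the DSMB to see data by group, including medical history, and to ask for more. This is optional, and no hospitalisation or life-threatening-event comparison is defined.

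None of these is a by-arm count of hospitalisations or non-fatal life-threatening events.

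**4. Relatedness, side by side.** Section 9.2.1 says the causality assessment does not determine what is reported. Section 9.2.2 makes suspected causation a condition for everything except congenital anomalies. Section 9.3.2 promises FDA at least an annual summary of serious events assessed as not related, a class that Section 9.2.2 otherwise leaves uncollected. A site cannot follow all three.

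**5. How informative would a by-arm table be?** The documents give no event rate, so there is no planned figure to reproduce, and the rates below are assumptions. Table 1 gives n = 500 per arm. With the same rate p in both arms:

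half-width of the 95% CI for the difference = 1.96 × √(2p(1 − p)/500)

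For p = 0.05: 1.96 × √(2 × 0.05 × 0.95/500) = 1.96 × 0.01378 = 0.027.

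The last column is the power of a two-sided 0.05 two-proportion test, with variance pooled under the null, if the rate doubles from p to 2p. The same calculation with 100 per arm and rates 0.20 and 0.40 gives 0.876, which agrees with Table 5 (87.6).

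| Assumed rate p | Expected events per arm | 95% CI half-width (percentage points) | Power for a doubling |
|---|---|---|---|
| 1% | 5 | 1.2 | 0.255 |
| 2% | 10 | 1.7 | 0.458 |
| 5% | 25 | 2.7 | 0.852 |
| 10% | 50 | 3.7 | 0.994 |

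**The case against.** The strongest reply is that this is a deliberate and reasoned policy. Sections 9.1 and 9.2.1 say that fluconazole is approved and well characterised, that the trial is not powered for new safety signals, and that collection is therefore targeted. Correcting one sentence in Section 9.2.2 would not in itself oblige the sponsor to add an all-cause table. That is fair as far as it goes. It explains dropping non-serious events and narrowing SAE reporting. It does not make the endpoint statement true, and it gives no reason for leaving hospitalisations that are already asked about without a summary.

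Several stronger readings are tempting, and the documents do not support them:

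- *All life-threatening events are exempt.* They are not. Those that are unexpected and suspected to be drug-caused remain SAEs and are tabulated by arm.
- *Serious liver injury appears in no table.* Its laboratory component is covered by Exploratory Outcome 7 and the laboratory toxicity analysis. Section 9.2.3 also sends aggregate liver data to the DSMB.
- *Any already described reaction is excluded.* Section 9.1 mentions exfoliative dermatitis as a reported reaction, yet Section 9.2.2 gives it as an example of a collectable SAE. Expectedness is left to the investigator, and Section 9.2.1 says to report in case of doubt.
- *Torsades, syncope and seizure go unwatched.* Halting rule B counts them.
- *There is no check on harm in subjects without coccidioidomycosis.* Secondary Outcome 6 is a non-inferiority comparison of Day 22 response in all randomised subjects. It does not count serious events, but it is a planned check on net clinical outcome.
- *The missing table would settle the question of harm.* For example, 25 versus 40 hospitalisations out of 500 per arm (5% versus 8%) is a difference of 3.0 points with half-width 1.96 × √(0.05 × 0.95/500 + 0.08 × 0.92/500) = 3.05 points, an interval that includes zero.
- *The data are all in hand.* Life-threatening status is not among the items named for the visits, and the early-termination visit (Section 7.4.1) does not name hospitalisations.

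**Conclusion.** The concern stands in a limited form. One of the two event types that Section 9.2.2 calls efficacy endpoints is not one. As written, the plan has no by-arm summary of hospitalisations or non-fatal life-threatening events unless each is judged unexpected and suspected to be drug-caused. Sections 9.2.1, 9.2.2 and 9.3.2 also disagree about the role of relatedness. Death is not part of the gap, and liver and QT-related events are partly covered elsewhere.

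The number of events affected cannot be stated, because the documents give no rate. At the assumed rates of 1% to 10%, a by-arm table would range from purely descriptive to reasonably informative, the latter from about 5% upward. The conclusion rests on the text supplied. Section 11.4.4 announces a separate statistical analysis plan for the efficacy analyses. That plan could add such a summary, but nothing here plans one. This should be corrected. It does not affect the validity of the primary efficacy test.

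**What to change.** 1. In Section 9.2.2, remove life-threatening events from the efficacy-endpoint rationale, or define that endpoint in Section 3.2 and Table 11. Reconcile Sections 9.2.1, 9.2.2 and 9.3.2 so that sites have one statement of how relatedness bears on reporting.
2. In Section 11.4.3 and in the DSMB reports, add a by-arm table in the safety population of deaths and all-cause hospitalisations through Day 43, regardless of relatedness or expectedness, with the risk difference and 95% confidence interval. The source is the interim history and record review at Days 22, 29 and 43, with the same hospitalisation item added at early termination.
3. In the same table, show assisted ventilation by arm. Sites must already identify it as a discontinuation and rescue trigger, so it can serve as a marker of life-threatening events.

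The cost is a coded hospitalisation field, one table and the wording changes. A wider life-threatening category would need a further data item. The plan should say that the table is descriptive, since precision depends on an unknown rate. Expedited reporting and the clinical management rules stay as they are.
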